Study Protocol

Official Title: Promoting Health through Parent Empowerment and the Activation of Routines (Pro-PEAR)

ClinicalTrials.gov ID (NCT number): NCT05020366

Protocol Date: 12/12/2022

Scientific Background

Obesity disproportionately impacts children with Down syndrome. Despite serious comorbidities such as higher rates of type 2 diabetes and obstructive sleep apnea syndrome, obesity prevention efforts have been largely neglected within this population. As guided by the 6-SQuID framework, we: 1) defined the problem; 2) clarified causal/contextual factors; 3) identified mechanisms underlying change; and 4) identified how to most efficiently target the change mechanism. Our primary deliverable, a manualized intervention protocol for the PrO-PEAR intervention, will be optimized and tested for feasibility in this study.

Preliminary Data: The Facilitators and Barriers to Health in Young Children with Down syndrome (FaB Health Ds) survey data can help to inform intervention design and drive prioritization of intervention components. According to data collected during our pilot phase (N=33), nutrition and sleep are emerging as priority areas to target for the PrO-PEAR intervention. The World Health Organization (WHO) recommends toddlers consume 5 or more servings of fruits and vegetables per day, however, only 34% of our sample meet this recommendation per parent report. When asked how much quality sleep their child gets over a 24-hour period, less than half of all parents reported an estimate within the recommended range (11-14 hours). In contrast, most parents report that their children meet the recommendations for physical activity, in that they participate in at least 3 hours of activity each day. Most families reported meeting recommendations for sedentary behaviors, such as screen time and time spent restrained (e.g., in a device like a highchair) to 1 hour or less.

Preliminary data also suggest that parents may not be aware of their child's risk related to nutrition and sleep. Most parents are confident in their knowledge of nutrition recommendations (72%) and were "not at all concerned" with their child's consumption of fruits (67%) or vegetables (53%). Similarly, most parents were also confident in their knowledge of sleep recommendations (89%), yet only 22% considered their child's sleep to be problematic. These data signal a disconnect between parental confidence and/or knowledge of healthy behaviors and reports of their child's behavior. We plan to measure child behavior change in each Institute of Medicine obesity prevention priority over time and identify associations with parental knowledge, readiness for change, empowerment, and activation.

Study Objectives

[figure not shown]
This proposed pilot RCT aims:

- 1) To determine the feasibility of the Pro-PEAR intervention in terms of recruitment, randomization, retention, adherence, and acceptability.
- 2) Estimate the effects of the Pro-PEAR intervention on parent reported child health behaviors in each IOM obesity prevention area (nutrition, physical activity, sedentary behavior, sleep) over time as compared to an enhanced usual care group.

Study Design & Methods

We will recruit 24 parent/child dyads from the Down Syndrome Center of Western PA to participate in a pilot RCT. Inclusion criteria for child participants are being between the ages of 12-36 months and having a diagnosis of Down syndrome; parent participants must be ≥ 18 years old and able to speak English fluently. We are recruiting children 12-36 months as most children are able to self-feed and sleep through the night at this time, yet it precedes the rapid weight gain observed among children with Down syndrome.⁷ Sample size was determined based on prior recruitment efforts and data on number of children within this age range served at the clinic (~100). We will use a 2:1 randomization ratio for assignment to intervention versus control group status to gain more experience using the newly developed PrO-PEAR intervention (see Figure 3). Child health behavior in the areas of nutrition, physical activity, sedentary behavior, and sleep will be reported by parents, in addition to general health status and potential mechanisms of behavior change at baseline, 3-months (post-intervention) and 6-months (follow-up). We will track physical growth via chart review.

Figure 1. Randomization Plan

B.2.1.3. Treatment. We will test the feasibility of delivering the PrO-PEAR intervention and our ability to randomize to an enhanced usual care group. Participants randomized to enhanced usual care will receive feedback on health behaviors after baseline assessments and continue to receive usual care therapies outside of the study. The PrO-PEAR group will complete four in-person modules with an occupational therapist, each covering an IOM obesity prevention priority area: 1) Healthy Eating; 2) Sleep; 3) Sedentary Behavior; and 4) Physical Activity. Parents in the intervention group will also receive six telehealth visits of family-based coaching to help participants understand recommendations and adopt new, healthy routines.

B.2.1.4. Measures. A priori benchmarks for recruitment, retention, adherence, data collection and acceptability have been established to test the feasibility of the PrO-PEAR intervention. Potential issues in each of these areas have been identified with possible solutions for each barrier (see Table 1). Protocol adherence will be evaluated via review of sessions using clinician documentation. Intervention acceptability will be rated using the Treatment Acceptability Questionnaire (TAQ),⁷ a valid and reliable assessment of parental intervention acceptance. Intervention completers are designated as those completing 80% of sessions (≤ 8 of 10).

Table 1. Indicators of Feasibility and Acceptability

Topic	Benchmark	Plan if Benchmark is Not Met
Recruitment	>3 parent/child dyads per month	Partner with other Ds clinics
Retention	$\geq 80\%$ of consented dyads will complete ≥ 8 sessions	Parent focus group to identify issues
Adherence	$\geq 80\%$ clinician protocol adherence during 100% of sampled sessions	Update protocol and increase training
Data Collection	$\geq 80\%$ planned assessments collected among intervention completers	Evaluate burden and reduce as needed
Acceptability	$\geq 90\%$ of parent intervention completers rate intervention as acceptable ($>28/48$ on TAQ)	Parent focus group to optimize protocol

We will assess parent-reported child health behaviors, parental mechanisms of behavior change, and child anthropometrics and demographics over time (see Table 2). The knowledge test will be created using the World Health Organization's early childhood recommendations for obesity prevention. All other tools have been validated for use with parents of young children. For this study, we are specifically interested in parent factors that may influence behavior

change, as parents provide the opportunities, environment, structure and feedback that will determine a child's formation of healthy (or unhealthy) behaviors early in life. Data collected during this trial will inform intervention optimization to emphasize those mechanisms related to prioritized child behaviors.

Table 2. Intervention Measures

Assessment	Brief Description	Outcome
Facilitators & Barriers to Health: Down syndrome (FaB Health Ds) ⁸	100-item parent survey designed to describe habits and facilitators/barriers to health in young children with Down syndrome ($\alpha=.91$).	Parent-reported child nutrition, physical activity, sedentary behavior and sleep behaviors
Knowledge of Recommendations to Prevent Obesity in Young Children	10-item test to determine knowledge of recommendations for nutrition, activity, sedentary behavior and sleep	Parental knowledge of healthy behavior recommendations
Readiness, Efficacy, Attributions, Defensiveness, & Importance Scale – Short Form (READI-SF) ⁹	15-item Likert-scale survey in which higher scores indicate greater parental readiness to engage in treatment and readiness for change ($\alpha=.94$).	Parental readiness for change
Parent Empowerment and Efficacy Measure (PEEM) ¹⁰	20-item Brief Likert-scale and strength-based assessment of parental empowerment and efficacy ($\alpha=.92$).	Parental empowerment
Child Anthropometrics	Height, weight, body circumferences (waist, hip, arm, thigh)	Health status (growth)
Child Demographics	Age, medical diagnoses, service utilization, surgical history, race, ethnicity, household income	Health and socioeconomic status

B.2.1.4. Data Analysis. Feasibility data will be assessed using descriptive statistics (e.g., frequencies, means, percentages) and compared to a priori benchmarks. We will calculate bivariate correlations between demographics, intervention adherence, and outcomes to identify potential confounders or factors that may influence response to treatment. We will estimate effect sizes (Cohen's d) of child health behaviors and parental factors (knowledge, readiness, empowerment, activation) over time and between groups. Finally we will explore associations (bivariate correlations) between potential mechanisms of change (parental factors) and child behavior change scores. Parental factors significantly associated with child behavior change will be analyzed using multiple linear regression to identify significant predictors of child health behavior.

Eligibility Criteria

Inclusion criteria for child participants are being between the ages of 12-36 months and having a diagnosis of Down syndrome; parent participants must be ≥ 18 years old and able to speak English fluently. We are recruiting children 12-36 months as most children are able to self-feed and sleep through the night at this time, yet it precedes the rapid weight gain observed among children with Down syndrome.

Statistical Considerations

Feasibility data will be assessed using descriptive statistics (e.g., frequencies, means, percentages) and compared to a priori benchmarks. We will calculate bivariate correlations between demographics, intervention adherence, and outcomes to identify potential confounders or factors that may influence response to treatment. We will estimate effect sizes (Cohen's d) of child health behaviors and parental factors (knowledge, readiness, empowerment) over time

and between groups. Finally we will explore associations (bivariate correlations) between potential mechanisms of change (parental factors) and child behavior change scores. Parental factors significantly associated with child behavior change will be analyzed using multiple linear regression to identify significant predictors of child health behavior.

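### The definition of intervention completers prints ≤ 8 of 10 sessions where ≥ 8 is meant, reversing the denominator of two of the five feasibility benchmarks if it is applied as written

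*Combined protocol and SAP*

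**What the plan says.** Section B.2.1.3 Treatment describes two kinds of session for the intervention arm: "The PrO-PEAR group will complete four in-person modules with an occupational therapist", and "Parents in the intervention group will also receive six telehealth visits of family-based coaching".

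Section B.2.1.4 Measures then defines the completer group: "Intervention completers are designated as those completing 80% of sessions (≤ 8 of 10".

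In Table 1 the Retention row sets its own session threshold, with the sign the other way round: at least 80% "of consented dyads will complete ≥ 8 sessions". Two other rows take completers as their denominator:

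- Data Collection: at least 80% of "planned assessments collected among intervention completers".
- Acceptability: at least 90% "of parent intervention completers rate intervention as acceptable", meaning a score above 28 of 48 on the Treatment Acceptability Questionnaire.

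The Recruitment and Adherence rows do not use the term. Each row carries a remedial step under the column "Plan if Benchmark is Not Met". The Data Analysis section says that feasibility results will be compared with these benchmarks.

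**The concern.** The parenthesis says at most 8 sessions. Taken as printed, a family that attended nothing is a completer and a family that attended all 10 sessions is not. That cannot be meant, and it conflicts with the Retention row.

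The slip matters more than a typing error in background text because it sits in an operative definition. No other passage gives a number for completers, and the term fixes who is counted in two of the five benchmarks. One of these, acceptability, is named in the first study aim. If the symbol were carried into analysis code or a results table, both percentages would be computed on the wrong families. A remedial step (reviewing assessment burden, or convening a parent focus group) could then be triggered or missed for the wrong reason. In addition, anyone checking a reported completer analysis against the public protocol would find that the sensible rule, ≥ 8, departs from the written one.

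**Working it through.** **Inputs from the protocol.** 4 in-person modules and 6 telehealth visits (Treatment section); the 80% completer threshold (Measures section); 24 dyads, allocated as follows: "We will use a 2:1 randomization ratio for assignment to intervention versus control group status" (Study Design & Methods).

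**Reproducing the protocol's figure.** 4 + 6 = 10 sessions; 0.80 × 10 = 8. The number 8 of 10 is correct, so only the direction of the sign is in question.

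**The two readings compared.** A family can attend 0 to 10 sessions, which gives 11 possible counts.

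| Sessions attended | Completer under ≥ 8 | Completer under ≤ 8 |
|---|---|---|
| 0 to 7 | no | yes |
| 8 | yes | yes |
| 9 or 10 | yes | no |

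Ten of the 11 counts are classified differently; only 8 is classified the same way.

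**Illustration of size.** The intervention arm is 24 × 2/3 = 16 dyads. The protocol gives no expected attendance. Assume that each session is attended independently with the same probability p, so that sessions attended, X, follow a Binomial(10, p) distribution. The values of p are assumptions. The expected number of dyads in a group is 16 × P(X in that group).

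| Group | p = 0.80: probability | Dyads of 16 | p = 0.90: probability | Dyads of 16 |
|---|---|---|---|---|
| Intended, X ≥ 8 | 0.678 | 10.8 | 0.930 | 14.9 |
| Literal, X ≤ 8 | 0.624 | 10.0 | 0.264 | 4.2 |
| Wrongly excluded, X ≥ 9 | 0.376 | 6.0 | 0.736 | 11.8 |
| Wrongly included, X ≤ 7 | 0.322 | 5.2 | 0.070 | 1.1 |
| In both, X = 8 | 0.302 | 4.8 | 0.194 | 3.1 |

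At 0.90 the main effect is the loss of the best attenders. At 0.80 the two groups are almost equal in size but differ in membership, so the error would not show in the count.

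**Chance that the literal group is empty.** This requires all 16 dyads to attend 9 or 10 sessions, so the probability is P(X ≥ 9)^16:

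- p = 0.90: 0.7361^16 = 0.007
- p = 0.95: 0.9139^16 = 0.237
- p = 0.98: 0.9838^16 = 0.770

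**Effect on the Acceptability benchmark.** With n completers, the 90% benchmark needs at least 0.9n favourable ratings, rounded up. For n = 10 to 16, one unfavourable rating is tolerated (14/15 = 93%). For n = 1 to 9, none is (3/4 = 75%). Shrinking the group from about 15 to about 4 therefore removes the only margin the benchmark has.

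**The case against.** The strongest reply is that nobody would be misled. The word completer, the 80% figure and the Retention row all point to at least 8, and an analyst would reject a rule that admits families with no sessions. Nothing in the protocol shows the symbol being used in code or in a derived variable. This stands, and it is why the point is minor.

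A second reply is that the literal group above ignores the first half of the sentence. A family with 0 to 7 sessions has not completed 80%, so applying the words and the parenthesis together leaves only families with exactly 8 sessions. That is a fair alternative reading, and under it nobody below 8 is counted. It does not rescue the text: families with 9 or 10 sessions are still excluded, and the expected group is 4.8 dyads at p = 0.80 or 3.1 at p = 0.90.

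Third, the 80% phrase lacks the words at least, and the Retention row does not mention completers, so neither is formally a second definition. This is correct. The direction is inferred from the Retention row and from the ordinary sense of completing, but the inference is secure.

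Fourth, the attendance rates and the independence of sessions are assumptions, and the 77% chance of an empty group needs 98% attendance. No shift in either benchmark percentage is estimated, because that would require ratings or assessment completion by attendance level, which the protocol does not give. This also stands.

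Finally, the symbol might have been misread when the PDF was converted. The sign ≥ is read correctly elsewhere in the text, including the age criterion and the Retention row, so this is unlikely. One misread character cannot be ruled out without the source page.

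**Conclusion.** The inequality in the completer definition is reversed. The threshold of 8 of 10 reproduces; the sign contradicts the Retention row and the plain meaning of a completer. The error is minor, because the intent is recoverable and harm arises only if the symbol is applied as printed.

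In that case two of the five benchmarks, Data Collection and Acceptability, would use the wrong denominator. The illustration, about 4 dyads instead of about 15 at 90% attendance, rests on 16 intervention dyads and on assumed, independent attendance. Recruitment, Retention, Adherence, the sample size and the planned effect-size, correlation and regression analyses do not use the completer definition and are unaffected. No effect on the overall feasibility conclusion is claimed.

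**What to change.** Check the symbol on the source page. If it is printed as shown, change the parenthesis in the Measures section from ≤ 8 of 10 to ≥ 8 of 10, and add the words at least before 80% so that the wording fixes the direction as well. Apply that single definition to the Data Collection and Acceptability rows of Table 1 and to any analysis code or report that refers to completers. The cost is one character and two words, with no change to design, conduct or data collection.

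### The Table 1 retention benchmark counts all consented dyads although only the PrO-PEAR arm has sessions, so at the planned 16:8 split it cannot exceed 66.7% against the required 80%

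*Combined protocol and SAP*

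**What the plan says.** Study Design & Methods sets the size and allocation: "We will recruit 24 parent/child dyads from the Down Syndrome Center of Western PA to participate in a pilot RCT", and "We will use a 2:1 randomization ratio for assignment to intervention versus control group status".

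Section B.2.1.3 (Treatment) describes the two arms. For the intervention: "The PrO-PEAR group will complete four in-person modules with an occupational therapist", and "Parents in the intervention group will also receive six telehealth visits of family-based coaching". For the control: "Participants randomized to enhanced usual care will receive feedback on health behaviors after baseline assessments and continue to receive usual care therapies". No study session is described for the control arm.

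Section B.2.1.4 (Measures) then defines completion: "Intervention completers are designated as those completing 80% of sessions (≤ 8 of 10". Directly below, Table 1 sets the retention benchmark at 80% or more "of consented dyads will complete ≥ 8 sessions", with a parent focus group as the response to a miss. Two other rows of that table, Data Collection and Acceptability, restrict their denominators to intervention completers. The Retention row carries no such restriction.

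Retention is one of the feasibility domains named in the first study aim. The Data Analysis and Statistical Considerations sections both say that feasibility results will be compared with these pre-set benchmarks.

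**The concern.** The numerator of the retention benchmark can come only from the intervention arm, while the denominator covers both arms. Everyone recruited consents to a randomized trial, so the consented dyads include those later assigned to enhanced usual care. Those dyads have no sessions to complete and count as failures by construction.

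A feasibility benchmark is useful only if it separates good performance from poor. Followed literally, this one reports retention as not met and points to a parent focus group even if every intervention family attends every session. If the denominator is instead corrected after attendance is known, the benchmark is no longer the one fixed in advance.

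The sign in the completer definition adds a second inconsistency. Read literally, it excludes a family attending 9 or 10 sessions and admits one attending very few. The Data Collection and Acceptability benchmarks are both computed among completers, so the definition matters beyond the Retention row.

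**Working it through.** **Inputs**
- Dyads: 24 (Study Design & Methods).
- Allocation: 2:1, intervention to control (same section).
- Sessions: 4 in-person + 6 telehealth in PrO-PEAR, none in enhanced usual care (B.2.1.3).
- Benchmark: at least 80% of consented dyads completing at least 8 sessions (Table 1).
- Assumption: all 24 recruited dyads consent and are randomized, and the 2:1 split is achieved exactly. The randomization figure is not shown in the copy reviewed, so 16:8 is derived from the text.

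**The plan's own figure.** Sessions: 4 + 6 = 10. Cut-off: 0.80 × 10 = 8. The 8-of-10 count is reproduced; only the direction of the printed sign is at odds with Table 1.

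**Arm sizes.** 24 × 2/3 = 16 PrO-PEAR; 24 × 1/3 = 8 enhanced usual care.

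**Dyads needed.** 0.80 × 24 = 19.2, so 20. Check: 19/24 = 79.2% fails; 20/24 = 83.3% passes.

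**Most that can be achieved.** All 16 intervention dyads complete: 16/24 = 66.7%. Shortfall: 20 − 16 = 4 dyads.

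**A realistic good result.** 13/16 = 81.3% within the intervention arm scores 13/24 = 54.2% on the benchmark as written.

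**Sensitivity to the assumptions**

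| Departure (assumed) | Highest possible score |
|---|---|
| 26 consent, 24 randomized 16:8 | 16/26 = 61.5% |
| 28 consent, 24 randomized 16:8 | 16/28 = 57.1% |
| 30 consent, 24 randomized 16:8 | 16/30 = 53.3% |
| 25 randomized, blocks of 3, last block incomplete | 17/25 = 68.0% |
| 22 randomized, blocks of 6, last block incomplete | 16/22 = 72.7% |

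Loss between consent and randomization lowers the ceiling. An incomplete last block can raise it a little above two thirds, but not to 80% in these cases. If randomization were entirely unrestricted, the number assigned to PrO-PEAR would be binomial (24, 2/3), and the probability of 20 or more is about 5.9%. Even then, at least 20 of them would have to complete.

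**With the denominator limited to the intervention arm.** 0.80 × 16 = 12.8, so 13. 13/16 = 81.3% passes; 12/16 = 75.0% fails. The benchmark becomes attainable and can distinguish the two results.

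**The case against.** The strongest reply is that the intent is plain. The benchmarks are introduced as tests of the feasibility of the PrO-PEAR intervention, the row counts sessions that only that arm has, and the sentence above the table defines intervention completers by the same 8-of-10 count. A sensible analyst would probably use the intervention arm, and the percentage can be computed from the same data. This stands as a reading of intent. It does not repair the text: no section states the restriction, and two rows of the same table show that the denominator is narrowed in words when that is meant.

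The second reply is that little depends on it. Reporting is descriptive, there is no progression rule, and the plan describes its remedies loosely: "Potential issues in each of these areas have been identified with possible solutions for each barrier". The worst literal outcome is an unneeded focus group. This also stands, and it limits the weight of the point. It does not remove it, because the threshold belongs to a domain named in the first aim.

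Third, the two-thirds ceiling holds only when exactly two thirds of dyads are assigned to PrO-PEAR, and the text describes no blocking. That is correct, and the conclusion is conditional on the planned split.

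Fourth, the reversed sign is probably a slip, since the same sentence speaks of completing 80% of sessions. That is fair; it is secondary to the denominator.

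**Conclusion.** The concern holds. The retention benchmark is wrong as written: its denominator includes an arm that cannot contribute to its numerator. At the planned split the shortfall is 4 dyads with perfect attendance. This rests on 24 dyads consenting and being randomized 16:8; dyads who consent but are not randomized would make it worse. The point should be fixed, but its reach is confined to how one feasibility domain is judged. Treatment-effect estimates do not depend on it.

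The two printed versions of the session cut-off contradict each other and need to be reconciled in the same edit.

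**What to change.** Restate the Retention row as at least 80% of dyads randomized to PrO-PEAR completing 8 or more sessions, which means at least 13 of 16 at the planned split.

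This also moves the starting point from consent to randomization, so report separately the number of dyads who consent but are not randomized. Loss at that stage then stays visible.

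Reconcile the sign in the completer definition with the one in the Retention row, so that a single definition serves the Retention, Data Collection and Acceptability rows.

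The cost is one phrase, one reported count and one symbol, with no new assessments. The change should be dated, with a note of whether any attendance data had been seen when it was made.

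### The Data Collection benchmark covers only intervention completers, and no benchmark covers randomization or control follow-up, so it can read 100% with no control follow-up data

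*Combined protocol and SAP*

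**What the plan says.** Aim 1 in Study Objectives sets out to determine feasibility "in terms of recruitment, randomization, retention, adherence, and acceptability". Aim 2 is to estimate effects "over time as compared to an enhanced usual care group". B.2.1.3 Treatment adds that the trial will test "our ability to randomize to an enhanced usual care group".

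B.2.1.4 Measures then states: "A priori benchmarks for recruitment, retention, adherence, data collection and acceptability have been established". Randomization is not in that list, and Table 1 has the same five rows and no sixth. Its Data Collection row requires at least 80% of "planned assessments collected among intervention completers". Its Retention row requires at least 80% "of consented dyads will complete ≥ 8 sessions".

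The text above the table defines the completer set: "Intervention completers are designated as those completing 80% of sessions (≤ 8 of 10". The ten sessions are the four in-person modules and six telehealth coaching visits described in B.2.1.3, all given to the PrO-PEAR group. For controls, the same section says: "Participants randomized to enhanced usual care will receive feedback on health behaviors after baseline assessments", followed by usual care outside the study.

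Assessments at baseline, 3 months and 6 months are planned without restriction to one arm (Study Design & Methods). B.2.1.4 Data Analysis and Statistical Considerations both say that feasibility data will be summarized descriptively and set against the benchmarks, and that Cohen's d will be estimated over time and between groups.

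**The concern.** A control dyad has no sessions to complete, so it can never enter the Data Collection denominator. Intervention dyads that stop attending are also left out. What remains is the group most likely to return for assessment.

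No other row fills the gap. Recruitment is a monthly rate. Retention counts sessions, not assessments. Adherence is about clinicians following the protocol, and Acceptability is rated by intervention completers.

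Two things are at stake. First, part of Aim 1 (randomization) has no criterion against which the result can be compared. Second, the comparison in Aim 2 rests on about 8 control families, whose only planned study contact after the baseline feedback is the assessments themselves. A larger trial would need to know whether such families can be followed. As written, the trial can report its data-collection benchmark as met whatever happens to them, and the response that Table 1 attaches to a missed benchmark would not be triggered.

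**Working it through.** The 80% in Table 1 is a chosen threshold and the sample size is pragmatic, so there is no calculated figure to reproduce. The check is on denominators.

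**Inputs from the protocol.** 24 dyads, 2:1 allocation and three assessment times (Study Design & Methods); ten sessions, PrO-PEAR arm only (B.2.1.3); 80% thresholds (Table 1).

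**Assumptions.** All 24 consented dyads are randomized, split 16:8. Each dyad-visit counts as one assessment. Every dyad gives a baseline. A completer has at least 8 of 10 sessions. The documents give no attrition rate, so the cases below are illustrations, not forecasts.

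**Planned assessments.** 24 × 3 = 72, of which 48 are intervention and 24 control. Follow-up visits: 24 × 2 = 48, of which 32 are intervention and 16 control.

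**Current benchmark** = collected among completers ÷ planned among completers. Take all 16 intervention dyads as completers, fully assessed, so that 48 intervention and 8 control baseline assessments are in hand:

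| Control follow-up | Table 1 benchmark | All randomized dyads |
|---|---|---|
| 16/16 | 48/48 = 100% | (48 + 8 + 16)/72 = 100% |
| 8/16 | 48/48 = 100% | (48 + 8 + 8)/72 = 89% |
| 0/16 (boundary) | 48/48 = 100% | (48 + 8 + 0)/72 = 78% |

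With 13 completers, the other 3 intervention dyads and all controls at baseline only, the benchmark is still 39/39 = 100%, against (39 + 3 + 8)/72 = 50/72 = 69% of all planned assessments.

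**Would a pooled trial-wide denominator be enough?** For follow-up visits, 80% of 48 is 38.4, so 39 are needed. That is met by 32/32 intervention plus 7/16 control (44%). It is not enough; the criterion has to hold in each arm.

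**Arm-specific thresholds.** 0.8 × 32 = 25.6, so 26/32. 0.8 × 16 = 12.8, so 13/16.

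**Chance of meeting both arm-specific lines.** This is a binomial calculation with the arms independent, for different within-dyad correlations between the two visits. Under full correlation the lines become 13/16 and 7/8 dyads.

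| True capture | Independent visits | Correlation 0.5 | Fully correlated |
|---|---|---|---|
| 90% | 0.964 × 0.932 = 0.90 | 0.930 × 0.889 = 0.83 | 0.932 × 0.813 = 0.76 |
| 85% | 0.64 | 0.58 | 0.52 |
| 80% | 0.32 | 0.32 | 0.30 |

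If true control capture is 50%, the control line of 13/16 is met with probability 0.011, 0.032 and 0.035 respectively.

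**Randomization, using Table 1's own 80% as an example.** 0.8 × 24 = 19.2, so 20/24. This is met with probability 0.91, 0.71 and 0.46 at true rates of 90%, 85% and 80%.

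**Retention row, read over all consented dyads.** At most 16 of 24 can attend sessions, and 16/24 = 67%, so the 80% (20/24) cannot be met. Over the 16 PrO-PEAR dyads it would need 13 (0.8 × 16 = 12.8).

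**The case against.** The completer restriction has a readable purpose. The benchmarks are said to test the feasibility of the intervention, 2:1 allocation was chosen to gain experience with it, and the response to a missed Data Collection benchmark is to look at burden. Restricting to completers separates assessment burden from drop-out. Drop-out itself is addressed by Retention: over the PrO-PEAR arm, more than 3 non-completers out of 16 would already be a miss. This answers much of the complaint about intervention drop-outs. It does not touch control follow-up.

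Loss of controls would also be visible. With no control follow-up the between-group effect size could not be computed, and the plan already provides frequencies and percentages. No row of Table 1 is a binding go/no-go rule. All of that is right and limits the severity, but the plan frames feasibility as comparison with benchmarks, and none would register the loss.

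Finally, a pass/fail line on 8 control dyads is noisy. At a true capture of exactly 80%, both arms pass only about 30% to 32% of the time, and two control families missing both visits gives 12/16, a miss. This stands as a cost. Any benchmark on a point estimate is noisy at this sample size, which is why a miss should prompt review and no more.

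**Conclusion.** The concern holds. Data Collection as written does not respond to control follow-up at all: it can read 100% at any level of control capture, including none. Randomization, named in Aim 1 and again in B.2.1.3, has no benchmark.

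That the benchmark can read 100% with no control follow-up does not depend on the 16:8 split; only the all-randomized percentages (89% and 78% in the illustrations) do. The 0/16 case is a boundary, not a prediction.

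This should be corrected, but it does not undermine the trial. Assessments are planned in both arms, and descriptive reporting could reveal the loss. Two separate wording errors in the same text do not add to the severity: the Retention denominator, under which 80% is out of reach if read literally, and the completer definition, whose inequality sign runs opposite to the one in the Retention row.

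**What to change.** 1. **Data Collection.** Require at least 80% of planned 3- and 6-month assessments among all randomized dyads, met separately in each arm and pooled over the two visits (26/32 and 13/16 if 24 are randomized 16:8; recompute the counts if fewer are). Report capture by arm and visit alongside, because pooling can hide a weak 6-month visit: 8/8 then 5/8 still gives 13/16. A miss should trigger review, not stop the program.
2. **Retention and completers.** State the Retention denominator as dyads randomized to PrO-PEAR, and reconcile the two session thresholds so that they point the same way.
3. **Randomization.** Add a row for the proportion of consented dyads who are randomized and accept their allocation, with a threshold that the sponsor sets before enrolment and counts by arm. Table 1's own 80% would mean 20/24.
4. **Optional, Acceptability.** Request the TAQ from every PrO-PEAR parent who received any session. Keep the completer figure as the benchmark and show beside it the figure for all these parents as a range, counting non-responders first as not acceptable and then as acceptable. This should not become a pass/fail rule: with non-responders counted as not acceptable, 90% of 16 would need 15 parents.

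The cost is wording in Table 1, one added row and, if item 4 is adopted, a few more TAQ requests. No visit, treatment or sample size changes. The benchmarks become harder to meet: at 90% true capture in both arms the new Data Collection rule passes with probability 0.76 to 0.90, and at 85% with 0.52 to 0.64. In return, true control capture of 50% would pass the control line with probability of only 0.01 to 0.04. If a pass/fail line on 8 controls is thought too noisy, reporting by arm and visit is the minimum to keep.
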